7.1 Diseases and Therapeutic Area

7.1.1 Acute Lymphoblastic Leukemia (ALL)

Paediatric ALL is a heterogeneous hematologic malignancy characterized by the proliferation of immature and abnormal lymphoid cells in the bone marrow and peripheral blood. The proliferation of these immature/abnormal lymphoid cells in the bone marrow subsequently prevails over the production of normal bone marrow elements ultimately resulting in decreased red blood cells, white blood cells (WBCs) and platelet counts (NCCN Clinical Practice Guidelines, 2014). ALL is the most common cancer diagnosed

in children with an incidence of about 4 per 100,000 children per year (International-Berlin-Frankfurt-Muenster study group [I-BFM SG], 2010). There has been a gradual increase in the incidence of paediatric ALL in the past 25 years. (McNally and Eden, 2004), Since 15% of children die from the disease, ALL is the most frequent cause of death in childhood malignancies (Gaynon, 2005).

Therapy for paediatric ALL is usually stratified according to risk characteristics in order to ensure that appropriate intensity of treatment is administered to patients with high-risk of relapse, while avoiding unnecessary toxicity in patients at lower risk (Schrappe and Stanulla, 2003) (Möricke et al, 2008). Despite the improvement in paediatric leukemia outcome with risk-based therapy, approximately 15% to 20% of paediatric leukemia patients will experience relapse of the leukemia. At the time of relapse, a combination of chemotherapy, novel immunotherapies and allogenic stem cell transplant is used to achieve a second remission (Cooper and Brown, 2015; Locatelli et al, 2012).

The classic prognostic features for B-precursor ALL are age at diagnosis and the leukocyte count, which were combined to create the Uniform Risk Classification to predict the risk of relapse. Children aged 1-9 years have a better outcome than infants, adolescents, or adults (Conter et al, 2010; Pui and Evans, 2006; Pui, 2008b; National Cancer Institute, 2014), while increasing leukocyte count predicts a poorer outcome .It should be noted that the Uniform Risk Classification is applicable only to B cell disease, fails to predict relapse in a third of standard-risk cases, and does not distinguish between high-risk and very high-risk disease, making further refinements necessary (Pui, 2008a).

Prognosis is further assessed after induction treatment based on MRD (the presence of a low number of leukemic cells that are not detectable by light microscopy). The detection of MRD after treatment has been shown to portend a higher prognostic value than variables identified at diagnosis and guide physicians to select the most favorable consolidation treatment option (ie, additional chemotherapy or alloHSCT) (Bassan and Hoelzer, 2011). In particular, the detection of MRD after induction therapy and/or consolidation therapy is an independent prognostic factor for poor outcome of ALL.

7.1.2 Treatment

In general, paediatric treatment regimens are more intense than those employed in adults and include courses of combination chemotherapy, and for patients at risk for or

with CNS involvement, specific local therapy (eg, intrathecal chemotherapy with or without cranial radiation). Treatment regimens for acute paediatric leukemia in the relapsed and refractory setting usually consists of 3 phases; induction, consolidation, and alloHSCT. All treatment regimens should also include CNS prophylaxis and/or treatment whenever appropriate.

Induction Therapy

The goal of induction therapy is to reduce tumor burden by clearing as many leukemic cells as possible from the bone marrow. Induction regimens are typically based on a standard backbone consisting of a combination of drugs including but not limited to: corticosteroids, vincristine, anthracyclines, clofarabine, cytarabine, mitoxantrone, etoposide, methotrexate, and thioquanine, and with or without L-asparaginase and/or cyclophosphamide, 6-mercaptopurine, and cytosine arabinoside.

Consolidation

The intent of post-induction consolidation is to eliminate potential leukemic cells that remain after induction therapy, thus permitting further eradication of residual disease. The combination of drugs and duration of therapy for consolidation regimens vary between studies and patient populations.

AlloHSCT

Patients with poor outcome and high rates of subsequent relapse after conventional intensive chemotherapy have an indication for alloHSCT from a matched donor or in case of very high-risk also from HLA-disparate donor. For a successful alloHSCT, the remission quality should be good, which may be the case after induction and early consolidation therapy. A low MRD value before alloHSCT predicts a better outcome after the allograft (Bader et al, 2009).

CNS Prophylaxis and Treatment

For patients at risk for, or with detection of CNS involvement at diagnosis, specific local therapy (eg, intrathecal chemotherapy with or without cranial radiation) is administered. The aim of CNS prophylaxis and/or treatment is to clear leukemic cells from sites that cannot be readily reached by systemic chemotherapy due to the blood-brain barrier, with the overall goal of preventing CNS disease or relapse. CNS specific therapy may include cranial irradiation and intrathecal chemotherapy (eg, methotrexate [MTX], either administered alone or in combination with cytarabine and steroids). CNS prophylaxis is

typically given throughout the course of ALL therapy starting from induction and continuing through consolidation.

Among paediatric patients with ALL, more than 95% achieve a first complete remission (CR1) with treatment and 75% to 85% remain disease-free 5 years after the initial diagnosis. Currently, about 15%-20% of patients suffer a relapse of ALL (Schrappe et al, 2013).

The prognosis for a patient with relapsed ALL mainly depends on the time elapsing from diagnosis to relapse, site of relapse, as well as cytogenetics and immunophenotype (Chessells et al, 2003; Uderzo et al, 2007; Malempati et al, 2007). The risk-group stratification of children with relapsed ALL (standard risk [SR] versus high-risk [HR] depends on time elapsing from diagnosis to relapse, and the immunophenotype (Locatelli et al, 2012).

Overall Survival (OS) rates after marrow relapse range from less than 20% for patients with marrow relapses occurring within 18 months from diagnosis to 40% to 50% for those whose relapses occur more than 36 months from diagnosis (Einsiedel et al, 2005; Nguyen et al, 2008). For patients with isolated CNS relapses, the OS rates for early relapse (< 18 months from diagnosis) are 40% to 50%, while they are 75% to 80% for children with late relapses (> 18 months from diagnosis) (Nguyen et al, 2008; Barredo et al, 2006). There is no evidence that early detection of relapse by frequent surveillance (complete blood counts or bone marrow tests) in off-therapy patients improves outcome. (Rubnitz et al, 2005). New data from the Cancer Research United Kingdom Children's Cancer Group show that approximately 50% of patients with high-risk first relapse have a second relapse within 2 years (Parker et al, 2010).

Approximately 44% of paediatric patients with second marrow relapse and 27% of those with third marrow relapse achieve a subsequent CR. Five-year disease-free survival rate in CR3 was reported to be 15% (Ko et al, 2010).

Fifteen to 20% of children with ALL die from treatment-resistant or recurrent ALL or from the acute and or long-term adverse effects of therapy (Pui and Evans, 2006; Stary et al, 2014). Two percent of children (Pui, 2008a) with ALL who do not achieve a remission are classified as having refractory disease and, often, suffer an even worse prognosis compared to patients with relapsed ALL (Schrappe et al, 2013).

7.1.2.1 Toxicity From Chemotherapy Agents Used to Treat Relapsed/Refractory Acute Lymphoblastic Leukemia

Major toxicities known to occur with chemotherapeutic agents used to treat childhood leukemia include:

Agent	Effects
Asparaginase	Hypersensitivity reactions, pancreatitis, thrombosis
Clofarabine	Cardiotoxicity, cytokine release syndrome, hepatotoxicity (including sinusoidal obstruction syndrome), pancreatitis, nephrotoxicity
Corticosteroids	Hypertension, hyperglycemia, osteonecrosis, fluid retention, psychosis
Cyclophosphamide/Ifosfamide	Nephrotoxicity, hemorrhagic cystitis, hyponatremia, fluid retention
Cytarabine	Conjunctivitis, flu-like symptoms
Doxorubicin/daunorubicin/mitoxantrone	Cardiotoxicity, benign red urine
Etoposide	Nephrotoxicity, hepatotoxicity, hypersensitivity reactions
Mercaptopurine	Hepatotoxicity
Methotrexate	Mucositis, nephrotoxicity, hepatotoxicity, encephalopathy
Thioguanine	Hepatotoxicity (including sinusoidal obstruction syndrome and portal hypertension)
Vincristine	Syndrome of inappropriate diuretic hormone, neuropathy (foot/wrist drop, paresthesia, constipation, ptosis, vocal cord paresis)

Table 7-1. Toxicities Expected With Chemotherapy

In addition, most of these agents also cause bone marrow suppression that results in pancytopenias (neutropenia, anaemia, and thrombocytopenia) and dermatologic/hair issues (alopecia).

7.1.3 Blinatumomab

Blinatumomab belongs to a new class of bispecific antibody constructs called bispecific T cell engagers (BITE[®]). Bispecific T cell engagers have been designed to direct T-effector memory cells towards target cells. The proximity induced by the BITE[®] triggers target cell-specific cytotoxicity, which closely resembles standard cytotoxic T lymphocyte (CTL) activation (Löffler et al, 2000; Wolf et al, 2005). Blinatumomab specifically targets cells that express CD19, a marker solely expressed by B cells, including B-precursor ALL cells. Blinatumomab recruits and activates T cells. These activated T cells then induce a half-maximal target B cell lysis (Dreier et al, 2002). Due

to its unique ability to redirect T cells via CD3 towards a CD19⁺ tumor cell lysis, blinatumomab can elicit repeated target cell elimination by cytotoxic T cells and a polyclonal response of previously primed CD4⁺ and C8⁺ T cells. The antitumor activity is effective within a wide range of effector to target (E:T) ratios.

In the absence of CD19⁺ target cells neither cytotoxicity nor release of cytokines will occur. Blinatumomab acts strictly in a target cell specific and dependent manner, with regard to cytotoxic action. The presence of both CD19⁺ target cells and T cells are required for its cytotoxic activity.

Blinatumomab received accelerated approval from the Food and Drugs Agency (FDA) for the treatments of adults and children with relapsed/refractory Philadelphia chromosome negative (Ph-) B-cell ALL in 2014: this was converted to full approval in 2017. The European Medicines Agency (EMA) granted conditional approval to blinatumomab for the treatment of adults with relapsed/refractory Ph- B-cell ALL in November 2015, with conditional approval converted to full approval in June 2018. Blinatumomab is indicated as monotherapy for the treatment of paediatric patients aged 1 year or older with Philadelphia chromosome negative CD19 positive B-cell precursor ALL which is refractory or in relapse after receiving at least 2 prior therapies or in relapse after receiving prior allogeneic hematopoietic stem cell transplantation.

The most serious adverse reactions that may occur during blinatumomab treatment include: infections (24.8%), neurologic events (13.8%), neutropenia/febrile neutropenia (10.1%), cytokine release syndrome (3.3%), and tumour lysis syndrome (0.7%). The most common adverse reactions were: pyrexia (69.2%), infusion-related reactions (43.4%), infections – pathogen unspecified (42.1%), headache (32.9%), anaemia (22.8%), thrombocytopenia (20.9%), febrile neutropenia (20.2%), oedema (20.0%), neutropenia (19.7%), rash (16.7%), increased liver hepatic enzymes (16.1%), backerial infectious disorders (15.4%), tremor (15.2%), cough (15.1%), leukopenia (13.4%), back pain (13.3%), chills (13.0%), hypotension (12.8%), viral infectious disorders (12.7%), decreased immunoglobulins (12.5%), cytokine release syndrome (11.6%), tachycardia (11.3%), insomnia (10.7%), fungal infectious disorders (10.6%), and pain in extremity (10.2%).

Amgen is currently assessing long-term safety, efficacy, and survival status in the Study 20120215: a randomized, open-label, controlled phase 3 trial to investigate the efficacy, safety, and tolerability of blinatumomab as consolidation therapy versus conventional consolidation chemotherapy in paediatric patients with B-precursor ALL.

7.2 Rationale

Study 20180130 is an observational study which will collect data on clinical outcomes on B-precursor ALL patients, treated with either blinatumomab or chemotherapy prior to alloHSCT whilst < 18 years, for a follow-up period of ≤ 12 years. The study will allow for the opportunity to investigate long-term outcomes, specifically neuropsychomotor development impairment, endocrine impairment, neurological impairment, and immune system impairment, HSCT-related AEs, relapse, long-term AEs, secondary malignancy formation, as well as OS.

Long-term impact of blinatumomab from paediatric clinical trials is relatively limited. The pivotal study MT103-205 is a single-arm multicenter phase II study preceded by dose evaluation to investigate the efficacy, safety, and tolerability of blinatumomab in paediatric and adolescent patients with relapsed/refractory B-precursor ALL. The median follow-up for the pivotal study MT103-205 is about 2 years. Study 20120215 is a randomized, open-label, controlled phase 3 trial to investigate the efficacy, safety, and tolerability of blinatumomab as consolidation therapy versus conventional consolidation chemotherapy in paediatric patients with high-risk first relapse B-precursor ALL. Study 20120215 will provide a long-term follow-up of 3 years. However, the long-term impact of blinatumomab beyond 3 years in paediatric patients is largely unknown.

The 3 major toxicities of blinatumomab are cytokine release syndrome (CRS), neurologic events, and infections. CRS has been observed in the R/R ALL indication in patients with high tumor burden at the start of blinatumomab treatment. CRS is generally an immediate event occurring upon initiating T cell therapy. Similarly, neurologic events are most frequently observed at the beginning of treatment and most clinically resolve, however, the exact mechanism of neurotoxicity is not well defined and the impact, particularly on children younger than two years, is unknown. The blood-brain barrier mechanism in infant is still immature or "leaky", rendering the developing brain more vulnerable to drugs, cytokines and other pathological conditions which could contribute to cerebral damage and neurological disorders. It is totally unknown if blinatumomab crosses the blood brain barrier and to which extent in infants; and what would be the consequence of its passage to the developing brain. Only 10 children under 2 years participated in the pivotal Study MT103-205 and no more than 20 children were of age between 2-6 years where neurotoxicity could also significantly and irrevocably alter brain functioning in the future.

Long term effect of impact of blinatumomab-mediated T-cell activation and its attack on CD-19-positive B cells including normal and malignant B-cells, in particular when considering developing immune system in children, is also unknown and needs to be observed, including an effect of vaccination with live vaccines.

Endocrine complications are among the most common chronic health conditions encountered following haemopoietic stem cell transplant (HSCT) and include thyroid dysfunction, osteoporosis, metabolic syndrome, growth impairment and gonadal dysfunction. The risk of these complications is influenced by pre-HSCT therapeutic exposures, transplantation-related conditioning and post-transplantation management of GvHD. The effect of blinatumomab on the endocrine system, notably followed by HSCT, needs to be evaluated.

Due to these gaps in knowledge this study is a post authorization safety study (PASS) and is category 1 regulatory commitment to the EMA. The current study will allow long-term real-world clinical data to be collected on relevant outcomes to address these uncertainties.

7.3 Statistical Inference

The study will compare blinatumomab therapy versus chemotherapy for the occurrence of neuropsychomotor developmental impairment, neurological impairment, endocrine impairment, and immune system impairment.

8. Research Question and Objectives

The overarching aim of this study is to describe and compare the long-term safety profile of B-precursor ALL paediatric patients who have been treated with either blinatumomab or chemotherapy prior to undergoing alloHSCT.

Primary 8.1

Primary Objective					
Objective	Endpoint				
 To estimate incidence of neuropsychomotor developmental impairment, endocrine impairment, neurological impairment, and immune system impairment (including auto-immune disorders and vaccine failure) 	 Impairment defined as any of the following: Neuropsychomotor development impairment in any area of social and emotional, language/communication, cognitive, or motor Neurologic impairment defined as any peripheral nervous system disorders including neuromuscular junction disorders; central nervous system disorders Endocrine impairment defined as any Hypothalamus-Pituitary-Gonadal Axis disorders; Hypothalamus-Pituitary-Adrenal (HPA) Axis disorders; Hypothalamus-Pituitary-Thyroid Axis disorders Immune system impairment defined as any leukopenia (neutropenia and/or lymphopenia); low IgG; low IgM, and; low IgA; autoimmune disorders; vaccination failure 				

8.2	Secondary
•	

• To estimate the incidence of Haemopoietic Stem Cell Transplant (HSCT) related adverse events (AEs)	 HSCT-related AEs defined as any second malignancy; Graft versus Host Disease (GvHD); infection, and/or; relapse
 To estimate the incidence of subsequent relapse of leukemia including in the central nervous system (CNS) 	 Relapse is defined as any of the following: Isolated bone marrow relapse (M3³ in the absence of extramedullary involvement) Combined bone marrow response (M2 or M3 marrow and at any extramedullary manifestation of ALL) Extramedullary relapse (either CNS relapse, testicular relapse, or relapse at other sites⁴)

³ Cytological bone marrow assessment grading: see Appendix F for details
 ⁴ See Appendix F for relapse criteria (including extramedullary relapse)

 To estimate the cumulative incidence of long-term AEs 	 AEs in any of the following organ systems: gastrointestinal, hematologic, dermatology, cardiac, pulmonary, hepatic, renal, neurological, infection, immunology, and skeletal
To estimate the incidence of secondary malignant formation	 Tumor type and anatomical site of tumor
To estimate overall survival	Estimate overall survival

9. Research Methods

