9.2.1 Study Period

Enrolment of patients into 20180130 will occur if they meet all eligibility criteria. All eligible patients or their caregivers/legal guardians will be approached to provide informed consent for participation. Once informed consent has been given, and all inclusion/exclusion criteria are met, the patient will be enrolled via interactive response technology (IRT) in the study and data collection will begin. The study will commence at the first data collection of the first site. Patients will be followed for a maximum of a 12-year period or up to the age of 25 years, death, withdrawal of consent, or loss to follow-up, whichever comes first. The study will end when 12 years of follow-up for the last patient (if the patient has not withdrawn consent, been lost to follow-up, or died before the end of the 12 years of follow-up) is completed. If the last patient enrolled on study dies or is lost to follow-up before the 12 years following alloHSCT, the remainder

of the patients on study will continue to be followed until all patients on study have reached 12 years following alloHSCT, until death, withdrawal of consent, or lost to follow-up, whichever occurs first.

Data will be entered into an eCRF and will encompass information abstracted from patient charts from routine clinical visits. Data abstraction will be performed approximately every 6 months (± 30 days) starting at enrolment. Additional data on neuropsychomotor development will be assessed through specific questionnaires (paper and/or electronic) which will be administered at pre-specified intervals starting at enrolment (approximately every 6 months [± 30 days] for patients up to 6 years old and approximately yearly [± 60 days] for patients from 6 years old).

The first day of follow-up (day 1) will be the date of successful completion of alloHSCT (following chemotherapy/ blinatumomab treatment).

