9.2.5 Study Follow-up

This is a prospective study where data will be collected at routine clinical visits which will occur per standard of care (for a period of up to 12 years). A total of 12 years follow-up or 144 months of follow-up is planned for study 20180130. At each data collection stage, relevant information will be retrieved from patient charts subsequent to the preceding data abstraction time point to ensure there is no gap in data collection. Data abstraction will be performed approximately every 6 months (± 30 days) starting at enrolment. Additional data on neuropsychomotor development will be assessed through specific questionnaires (paper and/or electronic) which will be administered at pre-specified intervals starting from enrolment (approximately every 6 months [± 30 days] for patients up to 6 years old and approximately yearly [± 60 days] for patients from 6 years old). For each enrolled patient, data collection will end at 12-years of follow-up, the age of 25 years, loss-to-follow-up, withdrawal of consent, or death, whichever occurs earliest. All treatments for ALL will be captured in this period.

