Regulation (inhibit, self-monitor), Emotion Regulation (shift, emotional control), and Cognitive Regulation (initiate, working memory, plan/organize, task monitor, organization of materials). For patients ages 19+, the informant report form will be completed by a parent (guardian) or other adult who knows the patient well (BRIEF-A Informant); skills are evaluated in the areas of Behavioral Regulation (inhibit, shift, emotional control, self-monitor) and Metacognition (initiate, working memory, plan/organize, task monitor, organization of materials). The BRIEF will be re-administered to patients ages 2-5 years every 6 months in order to capture the more rapid rate of typical development; parents (guardian) or informants of patients ages 6 years and older will complete the form every year.

- A complete written manual describing administration and scoring procedures will be created by study neuropsychologist who has thorough knowledge of and experience with these measures. Initial personalized training of these procedures with study personnel will also be provided, along with ongoing consultation as needed.
- Neurological impairment defined as:
 - Peripheral nervous system disorders (including neuromuscular junction)
 - Central nervous system disorders
- Endocrine impairment defined as:
 - Hypothalamus-Pituitary-Gonadal Axis disorders
 - Hypothalamus-Pituitary-Adrenal (HPA) Axis disorders
 - Hypothalamus-Pituitary-GH Axis disorders
 - Hypothalamus-Pituitary-Thyroid Axis disorders
- o Immune system impairment defined as:
 - leukopenia (neutropenia and/or lymphopenia)
 - Iow IgG
 - low IgM
 - low IgA
 - Autoimmune disorders
 - Vaccination failure

Secondary Objectives

- HSCT-related AE defined as any second malignancy; Graft versus Host Disease (GvHD); infection, and/or; relapse
 - o Acute GvHD data includes
 - Grading of disease by either National Institute of Health (NIH) or Seattle Criteria
 - Organ involvement: skin; gut; liver; lung; eye; mouth' musculoskeletal, and/or; other

- GvHD associated symptoms: thrombocytopenia (<100 G/l); eosinophilia (Absolute Eosin Count: AEC > 500x10/L); bronchiolitis obliterans; bronchiolitis obliterans organizing pneumonia (BOOP); polyserositis, and; other
- Resolution
- Chronic GvHD data includes:
 - Diagnosis based upon clinical or histological evidence
 - Diagnosis of progressive, quiescent, or de novo disease
 - Grading of disease by either NIH or Seattle Criteria

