9.5 Study Size

The targeted sample size for this study is approximately 298 patients. However, the actual number of patients that will be included in the study will depend on the results of site feasibility, willingness of patients (or their legal guardians/caregivers) or sites to participate in the study.

According to Marshall et al 2013, paediatric ALL patients are expected to have toxicity during intensification of therapy, generally related to hematological counts (Marshall et al, 2013). All patients also expect to have some immune complications after treatment end (Perkins et al, 2017) that will persist for some time.

Assuming that between 85%-98% of all patients will have at least one event, the expected ranges of sample sizes and relevant 95% CI is provided below. If 100 patients are enrolled.

95% C	onfidence	Interval o	of Estimated	Incidence o	of Adverse	Events by	Sample
-------	-----------	------------	--------------	-------------	------------	-----------	--------

S	ize	

Enrolled N Per Arm	Estimated Incidence of events	95% Confidence Interval*
150	98%	94.3%-99.3%
150	90%	84.1%-93.9%
150	85%	78.4%-89.8%
100	98%	93%-99.5%
100	90%	82.5%-94.5%
100	85%	76.7%-90.7%
75	98%	90.8%-99.3%
75	90%	82.0%-95.4%
75	85%	75.6%-91.6%
50	98%	89.5%-99.7%
50	90%	78.6%-95.7%
50	85%	71.5%-91.7%

* Wilson score interval

Sample size calculation for comparison analyses was calculated based on the number of long-term survivors needed. A risk difference of 10% (98% vs 88%) is considered as clinically significant. If the sample size is 52 long-term survivors per arm (104 in total), then a risk difference of as little as 10% will be detectable (p-value < 0.05).

Number of Long-term Survivors per Arm	Observed Risk Difference	P-value*
52/52	98% vs 88% = 10%	0.0455
40/40	98% vs 86% = 12%	0.0477
30/30	98% vs 83% = 15%	0.0477
20/20	98% vs 77% = 21%	0.0444

* z-test of two proportion comparison

Assuming a 35% long-term survival rate, the required number of patients entering the study per arm is 149 (52/0.35). Therefore, the number of patients entering the study needed to successfully fulfill the primary objectives while taking into account the 35% survival rate is 298.

Even though long-term survivors contribute the most essential data to this study, all enrolled patients contribute important information. If the total sample size is 149 patients per arm (298 in total), then a risk difference of as little as 5% will be detectable (p-value < 0.05).

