9.6 Data Management

All data will be entered by sites into an eCRF that will be used to build the study database. Data abstraction will be done approximately every 6 months $(\pm 30 \text{ days})$ starting from enrolment. Additional data on neuropsychomotor development will be assessed through specific questionnaires (paper and/or electronic) which will be administered at pre-specified intervals starting at enrolment (approximately every 6 months [± 30 days] for patients up to 6 years old and approximately yearly [± 60 days] for patients from 6 years old) either in person or via telephone interview or mail. The score and percentiles from the questionnaires will be used for the final analysis. The final analysis cohort will be constructed from the complete review of inputted data documenting events in a patient's history from primary disease diagnosis until the earliest occurrence of the following events: death, withdrawal of consent, end of available data in the chart, completion of the 12-year follow-up period, or up to the age of 25 years. Data to be abstracted include variables relating to ALL diagnosis, ALL-associated treatment, development impairment, HSCT-associated AEs, leukemia relapse, long-term AEs, secondary malignancy until the earliest of: death, withdrawal of consent, end of available data in the chart, completion of the 12-year follow-up period, or 25 years of age.

Each patient will be assigned a unique identification number at the time of the first data entry. This unique identification number will be used to link data to subsequent data entries. The data will be abstracted by site staff from patient medical records into a web-based electronic data capture (EDC) system, using an electronic abstraction form that will provide an integrated, transparent tool to facilitate and record center recruitment, case identification, patient selection and study progress at the center and patient level.

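### The immune endpoint counts any leukopenia or low immunoglobulin from transplant onward, so it and the any-event quantity used for sizing are expected near the ceiling and say little about long-term immune deficit

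*Protocol*

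**What the plan says.** The endpoint table in Section 8.1 introduces four domains with "Impairment defined as any of the following" and gives the fourth as "Immune system impairment defined as any leukopenia (neutropenia and/or lymphopenia); low IgG; low IgM, and; low IgA; autoimmune disorders; vaccination failure". Section 9.3.1 repeats the immune items as a list beginning "leukopenia (neutropenia and/or lymphopenia"). Neither place attaches a grade, a duration or a time window to them. Neuropsychomotor impairment, by contrast, has a two-standard-deviation threshold in Section 9.3.1.

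On timing, Section 9.2.1 says: "The first day of follow-up (day 1) will be the date of successful completion of alloHSCT". Section 9.6 builds the analysis cohort from "events in a patient's history from primary disease diagnosis" onward, so the weeks after transplant are on record even when a patient enrols later. Section 9.2.5 states: "A total of 12 years follow-up or 144 months of follow-up is planned for study 20180130".

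Section 9.7.2.2.3 plans incidence proportions and Kaplan-Meier estimates of time to first onset for each specified event. Its only exclusion is for events after relapse or secondary malignancy.

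Section 9.5 says "All patients also expect to have some immune complications after treatment end" and that these will last for some time. It continues "Assuming that between 85%-98% of all patients will have at least one event". It then calls 98% versus 88% a clinically significant difference, takes 52 long-term survivors per arm, divides by 35% survival, and reaches 149 per arm, 298 in total.

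**The concern.** Section 7.2 explains why the study exists. The long-term effect of B-cell attack on a developing immune system is unknown and has to be observed. An endpoint met by any leukopenia or any low immunoglobulin class, at any time from transplant, mixes early and transient abnormalities with lasting deficits. Under a first-onset analysis only the first abnormality counts, and a later, persistent deficit in the same patient adds nothing to that analysis.

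The sizing has a related problem. It rests on the share of patients with at least one event. If nearly everyone in both arms has an immune event, that share has almost no room to differ between arms, and a real difference in the neurological, endocrine or developmental domains would be hidden inside it.

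**Working it through.** **1. The plan's own figure.** Inputs from Section 9.5: 98% versus 88%, 52 per arm, z-test of two proportions, 35% survival.
- Pooled proportion = (0.98 + 0.88)/2 = 0.93. Standard error = √(2 × 0.93 × 0.07 / 52) = 0.0500. z = 0.10/0.0500 = 2.00, two-sided p = 0.0457 (stated: 0.0455).
- 52/0.35 = 148.6, rounded up to 149; × 2 = 298. The stated size reproduces.

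**2. Consistency within Section 9.5.** A pooled any-event proportion cannot be lower than the proportion for one of its components. An arm at 88% therefore needs immune incidence of at most 88% in that arm. The same section expects immune complications in all patients. Both cannot hold for one definition of immune event and one observation window.

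**3. Ceiling.** Let q be immune incidence, equal in both arms. The pooled proportion lies between q and 1, so the largest possible difference between arms is 1 − q. The protocol gives no separate figure for q. I take its two planning values for at least one event, and the all-patients statement, as the range (an assumption):

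| q | largest possible difference |
|---|---|
| 85% | 15 points |
| 98% | 2 points |
| 100% | 0 (no non-events, so the planned odds ratio cannot be estimated) |

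**4. What the ceiling hides.** Assumed example: any of the other three domains occurs in 30% versus 50%, independently of immune events. Pooled proportion = 1 − (1 − q)(1 − o), where o is incidence in the other domains. Power = Φ[(d − 1.96 × SE0)/SE1], where d is the difference and SE0 and SE1 are the pooled and unpooled standard errors.
- q = 85%: 1 − 0.15 × 0.70 = 89.5% versus 1 − 0.15 × 0.50 = 92.5%. Power is 8% at 52 per arm and 15% at 149.
- q = 98%: 1 − 0.02 × 0.70 = 98.6% versus 1 − 0.02 × 0.50 = 99.0%. Power is 4% and 5%.
- Same contrast without the immune component, 30% versus 50%: power is 55% and 94%.

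**5. Precision away from the ceiling.** Section 9.5 tabulates Wilson intervals only for 85% to 98%. With z = 1.96, the interval is [p + z²/2n ± z√(p(1 − p)/n + z²/4n²)] / (1 + z²/n):

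| Incidence (assumed) | n = 149 | n = 52 |
|---|---|---|
| 10% | 6.1–15.9% | 4.4–21.1% |
| 20% | 14.4–27.1% | 11.4–32.8% |
| 30% | 23.2–37.8% | 19.3–43.5% |
| 40% | 32.5–48.0% | 27.8–53.6% |

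At 30% the half-width is (37.8 − 23.2)/2 = 7.3 points with 149 and (43.5 − 19.3)/2 = 12.1 with 52. The protocol's rows at 150 per arm have half-widths from (99.3 − 94.3)/2 = 2.5 to (89.8 − 78.4)/2 = 5.7 points.

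**The case against.** Several objections have force.

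- **Strength of the ceiling.** A reader might infer that every patient has the immune event on day 1 and that incidence is about 100% at once in both arms. The protocol does not say so. Its numeric range is 85% to 98%, its all-patients remark concerns the period after treatment and is not tied to day 1, and it gives no rate of leukopenia after conditioning. Sections 9.2.4 and 9.3.2 treat pre-transplant immune events as baseline, so a deficit already present at transplant need not count as a new onset. What remains is at or near the ceiling.
- **The domains are already separate.** Section 7.3 names four comparisons, and Section 9.7.2.2.3 summarises each specified event. The any-of line in Section 8.1 can be read as a header over four definitions. This stands: the pooled quantity does its work only in Section 9.5, and the other three domains are unaffected.
- **Late deficits are seen elsewhere.** It would be too strong to say they are never counted. Section 9.3.1 collects occurrence and severity of long-term haematologic and immunological adverse events, and Section 9.7.2.2.4 lists a possible subgroup with immune events in the first three years. Neither is the primary immune analysis, and the subgroup is optional.
- **The event may depend on treatment.** A reader might infer that the any-event rate is fixed by the transplant alone. The documents do not show this: Section 7.1.3 lists leukopenia (13.4%) and decreased immunoglobulins (12.5%) as blinatumomab reactions. A landmark used alone could discard early treatment-related events, so any-time incidence should be kept.
- **Detail for the analysis plan.** Laboratory cut-offs may properly be set there, and their absence is not the point. The protocol itself fixes any such event, the transplant-day clock and the sizing contrast.

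**Conclusion.** The point holds in this form: as defined, the immune domain and any at-least-one-event quantity containing it are expected at or near the ceiling, and a first-onset analysis of that domain is weak evidence on lasting immune deficit. Section 9.5 is also at odds with itself, since 98% versus 88% requires an arm in which at least 12% of patients have no immune event.

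The 1 − q bound assumes equal immune incidence in the two arms; if incidence differs, the pooled difference can be larger. Taking q from 85% to 100% is an assumption guided by Section 9.5. The power figures also rest on the assumed 30% versus 50% contrast and on independence. The precision table is not wrong for the range it covers; it simply does not reach incidences that other domains might have. The change should be made, but it does not invalidate the study, because three of the four primary domains remain informative.

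**What to change.** 1. For leukopenia and low immunoglobulin, base the long-term immune comparison on presence or new onset at or after a prespecified post-transplant landmark chosen by the clinical team, with one or two alternative landmarks as sensitivity analyses. Keep any-time incidence as a descriptive result so that early treatment-related events are not lost.
2. State in Sections 8.1 and 9.7.2.2.3 that the arms are compared by domain and not on the pooled any-event quantity. In Section 9.5, reconcile the expectation for all patients with the 98% versus 88% contrast.
3. Add precision rows at 10% to 40% incidence, labelled as an assumed range, for 149 per arm and for 52 survivors per arm.

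The cost is revised endpoint wording, a few table rows and some extra analysis. No study visit is added. The real drawback is that data come from routine care, so immunoglobulin values may be missing around the landmark. The share of patients with a value should be reported by arm.
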